## SRI-4, BICLA and LLDAS

The criteria for SRI-4, BICLA and LLDAS responses will be evaluated based on the non-missing and imputed PGA, hSLEDAI and BILAG data. If any criteria based on the non-missing and imputed PGA, hSLEDAI and BILAG data cannot be evaluated, then the subject will be considered as a non-responder.

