### **Lupus Low Disease Activity State (LLDAS)**

A subject achieves LLDAS response if all of the following criteria are met:

1. hSLEDAI  $\leq 4$  with no activity in major organ systems (renal [proteinuria, haematuria, pyuria, urinary casts], central nervous system (CNS) [seizure, psychosis, organic brain syndrome, cranial nerve disorder, CVA], cardiopulmonary [pericarditis, pleurisy], vasculitis, fever)
2. no new lupus disease activity (i.e. no new descriptor scores in hSLEDAI) compared with the previous assessment
3. PGA VAS (scale 0-3)  $\leq 1$
4. Current prednisolone (or equivalent) dose  $\leq 7.5$  mg/day
5. Standard maintenance doses of immunosuppressive drugs and approved biological agents (i.e. no increase or initiation of immunosuppressive drugs).

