#### Hybrid SLEDAI

In case of completely missing hSLEDAI assessment (e.g. missed visit) or partially missing (e.g. laboratory measurements not available), the missing post-baseline hSLEDAI total score will be imputed using last observation carried forward (LOCF) if the previous analysis visit is not missing. Baseline hSLEDAI will not be carried forward to post-baseline.

The hSLEDAI total score will then be computed based on the non-missing and imputed data. **If the hSLEDAI total score cannot be evaluated after imputation, the hSLEDAI score  $\geq 4$  points reduction from baseline will be considered not met.**

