## CLASI

**In case of completely missing CLASI assessment (e.g. missed visit) or partially missing, the missing post-baseline CLASI items will be imputed using LOCF if the previous analysis visit is not missing. Baseline CLASI will not be carried forward to post-baseline.**

**The CLASI activity score will then be computed based on the non-missing and imputed data. If the CLASI activity score cannot be evaluated after imputation, the CLASI activity score  $\geq 50\%$  improvement endpoint will be considered not met.**

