## BILAG

In case of completely missing BILAG assessment (e.g. missed visit), the missing post baseline BILAG item scores will be imputed using LOCF if the previous analysis visit is not missing.

In case of partially missing, missing laboratory items (e.g. UPCR, creatinine, etc.) will be imputed using LOCF if the previous visit is not missing; other missing items (e.g. active nephritis, Coombs' test positive, etc.) will be imputed as 'No' or 'Not Present'.

Baseline BILAG will not be carried forward to missing post-baseline BILAG.

The BILAG organ domain scores will be calculated based on the non-missing and imputed components. If the non-missing and imputed components are not sufficient to identify the organ domain score, worst scenario approach will be used to determine the BILAG organ domain scores.

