## LLDAS

Criteria	Derivation
HSLEDAI $\leq 4$ with no activity in major organ systems (renal, CNS, cardiopulmonary, vasculitis, fever)	HSLEDAI score $\leq 4$  proteinuria, haematuria, pyuria, urinary casts, seizure, psychosis, organic brain syndrome, cranial nerve disorder, CVA, pericarditis, pleurisy, vasculitis and fever in hSLEDAI are marked 'not present'
No new lupus activity compared with the previous assessment	No new 'present' hSLEDAI descriptors compared to previous visit
PGA $\leq 1$	PGA $\leq 1$

Current prednisolone (or equivalent) dose $\leq$ 7.5 mg/day	Prednisone equivalent is $\leq$ 7.5 mg/day at the visit
Standard maintenance doses of immunosuppressive drugs and approved biological agents (i.e. no increase or initiation of immunosuppressive drugs.)	No new or increase in immunosuppressant at the visit

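### The SAP does not say whether hSLEDAI is carried forward by descriptor or by total score; on the descriptor reading, LLDAS criterion 2 is met automatically when week 52 is fully missed

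*SAP*

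**What the plan says.** **The criterion.** SAP Section 5.6 defines LLDAS criterion 2 as "no new lupus disease activity (i.e. no new descriptor scores in hSLEDAI) compared with the previous assessment". The LLDAS table in Appendix B programs it as "No new 'present' hSLEDAI descriptors compared to previous visit". Criterion 1 also needs individual descriptors, because it requires a total of at most 4 "with no activity in major organ systems".

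**The imputation.** In SAP Section 8.3, under Hybrid SLEDAI, when an assessment is wholly or partly missing "the missing post-baseline hSLEDAI total score will be imputed using last observation carried forward (LOCF) if the previous analysis visit is not missing". The same paragraph goes on: "The hSLEDAI total score will then be computed based on the non-missing and imputed data". The neighbouring rules name the level explicitly. For CLASI, "the missing post-baseline CLASI items will be imputed using LOCF". For a fully missed BILAG, "BILAG item scores will be imputed using LOCF if the previous analysis visit is not missing". PGA is also carried from the preceding analysis visit.

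**The composite.** Under SRI-4, BICLA and LLDAS, the SAP says: "The criteria for SRI-4, BICLA and LLDAS responses will be evaluated based on the non-missing and imputed PGA, hSLEDAI and BILAG data". A subject with any criterion that still cannot be evaluated is a non-responder.

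**A parallel case.** The BILAG flare index is also a comparison with the preceding assessment. Section 8.3 leaves it missing when the whole BILAG is missing. LLDAS criterion 2 has no such provision.

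**The analysis.** After the futility stop, Table 9-2 reports LLDAS as a count and percentage by arm. Section 10 removes treatment comparisons.

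**The concern.** Criterion 2 asks about change between two visits, and carry-forward copies the earlier visit into the later one. Efficacy windows in Appendix D are four weeks apart, so week 48 is both the only source for a missed week 52 and its comparator. If descriptors are copied, the comparison sets week 48 against itself.

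This differs from an ordinary carried-forward response. The last observed LLDAS status can be a failure, and the missed visit turns it into a response. The two readings of the Hybrid SLEDAI paragraph also give opposite results for the same subject, so two programmers following the SAP could report different LLDAS rates.

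**Working it through.** The plan gives no figure on this point to reproduce. The check applies the SAP rules to a constructed subject and then to a grid of descriptor patterns.

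**Inputs from the SAP.** The Appendix B weights are low complement 2 and rash 2; neither is on the major-organ list in Section 5.6. LLDAS requires hSLEDAI at most 4, PGA at most 1 and prednisone-equivalent at most 7.5 mg/day.

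**Assumed subject.** Week 44: low complement only. Week 48: low complement plus new rash. PGA 0.8, prednisone 5 mg/day, no immunosuppressant change. Week 52 is fully missed.

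| Evaluation | Total | Criterion 1 | Criterion 2 | Criteria 3–5 | LLDAS |
|---|---|---|---|---|---|
| Week 48 observed, against week 44 | 2 + 2 = 4 | met | not met (rash is new) | met | no |
| Week 52, descriptors carried, against week 48 | 4 | met | met (record against itself) | met | **yes** |
| Week 52, total only carried | 4 | organ part not evaluable | not evaluable | met | **no** |
| Week 52, criterion 2 kept from week 48 | 4 | met | not met | met | no |

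**Which subjects can change.** Ten descriptors were used, with up to three present at each of weeks 44 and 48 and criteria 3–5 met. That gives 1 + 10 + 45 + 120 = 176 patterns per visit and 176 × 176 = 30,976 pairs. Of these, 30,343 fail LLDAS at week 48. With week 52 missed and descriptors carried, 3,415 of the 30,343 become responders. In every one, criterion 2 was the only week 48 failure. No failure on a total above 4 or on major-organ activity was reversed. The grid gives all patterns equal weight, so 3,415 out of 30,343 shows who is affected and is not a rate.

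**Size.** The share of an arm affected is P(week 52 missed, week 48 present) × P(week 48 fails on criterion 2 only). Neither probability is in the documents. Assuming 5–15% and 2–10%:

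- low: 0.05 × 0.02 = 0.001, or 0.1%
- high: 0.15 × 0.10 = 0.015, or 1.5%

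In an assumed arm of 25 evaluable at week 52, that is 25 × 0.001 = 0.025 to 25 × 0.015 = 0.375 subjects. If one such subject occurs, the arm's rate moves by 1/25 = 4 points, as it would for any single subject. The product omits that the steroid and immunosuppressant criteria must also hold at week 52, so it errs high.

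**The case against.** **The literal wording names the total.** The imputation sentence carries the total score, while the CLASI and BILAG rules name items. On that reading no descriptors exist at a missed week 52, the subject is a non-responder, and nothing flips. This stands as one of two readings. Against it, the paragraph then computes the total from filled-in data, which makes little sense if the total itself was filled in. The composite rule also expects LLDAS to be evaluated on imputed hSLEDAI.

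**Carry-forward assumes no change.** A subject seen at week 52 with the same descriptors as at week 48 would meet criterion 2, and week 48 LLDAS is not a listed primary or secondary endpoint. This is fair: passing is consistent with a stable state. But the data carried say nothing about new activity, and the SAP declines to make this inference for the flare index.

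**Few subjects qualify.** Protocol Section 8.1.2 asks subjects who leave to have a visit with week 52 procedures at least 6 weeks after the last dose. After a week 48 dose that is day 337 + 42 = 379, inside the week 52 window of days 351–394. Many late leavers would therefore have data. Subjects with no opportunity for week 52 because of termination are excluded. Both points stand and lower the frequency. They do not remove the pattern: six weeks after a week 40 dose is day 281 + 42 = 323, which falls in the week 48 window (323–350) and can leave week 52 empty.

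**A stronger inference to avoid.** A reader might conclude that missing week 52 can only help a subject on criterion 2, or that missed visits generally turn LLDAS failures into responses. The documents do not support this. On the total-only reading a missed visit counts against the subject. Carry-forward reaches back one visit, so if week 48 is missing too the result is non-response. Failures on other criteria are not reversed.

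**Conclusion.** The SAP leaves the level of hSLEDAI carry-forward open for LLDAS. If descriptors are carried, criterion 2 is met by construction at a fully missed visit, and a subject whose only week 48 failure was criterion 2 becomes a week 52 responder. If only the total is carried, that subject is a non-responder. This follows from the SAP text and does not depend on the assumed patient values.

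Severity is minor. The endpoint is secondary and descriptive, and no test, error rate or decision depends on it. The 0.1% to 1.5% of an arm rests on assumed probabilities and is probably high; the true frequency cannot be derived from the documents.

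**What to change.** In SAP Section 8.3 (Hybrid SLEDAI; SRI-4, BICLA and LLDAS) and the LLDAS table in Appendix B, state that hSLEDAI is carried forward at descriptor level, and add:

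*If the hSLEDAI assessment at the visit is completely missing, LLDAS criterion 2 keeps the result it had at the visit carried forward; if that is not available, criterion 2 is not met. If the assessment is only partially missing, any newly present descriptor observed at the visit counts as failure of criterion 2.*

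The last sentence is needed because Section 8.3 also imputes partly missing assessments. Without it, a subject seen with a new descriptor but lacking a laboratory result could inherit an earlier pass.

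The cost is a few sentences and a small change to the derivation code. The LLDAS rate may be slightly lower than with unqualified descriptor carry-forward. For a fully missed visit the carried total is the same at either level, so the hSLEDAI total used in SRI-4 and BICLA does not change. For partly missing assessments the level can change that total, so the choice should be made with those endpoints in view.

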## BILAG Flare index

**BILAG flare index will be evaluated based on BILAG scores. In case of partially missing BILAG assessment, imputed BILAG scores will be used. In case of completely missing BILAG assessment, BILAG flare index will remain missing.**

### **Tender and Swollen Joint Counts**

If a joint is excluded (non-evaluable or missing), the joint counts will be prorated based on the algorithm described below.

**Prorated Joint Counts:** If at least half but not all joints are evaluable (at least 14 joints for the total 28 joint count, at least 11 joints for the 22 hands and wrists joint count) then the observed prorated tender or swollen joint count will be calculated. The prorated scores will be adjusted based upon the number of evaluable joints: the counted score will be multiplied by 28 (for total) or 22 (for hands and wrists) as applicable and divided by the number of joints evaluated. If less than half of the joints are evaluable, the number of tender or swollen joints is missing. For example, if only 25 of the 28 joints are assessed at a visit and 10 of those 25 are tender/painful and 8 of those 25 are swollen, the prorated total joint counts are:

Tender:  $(10/25) * 28 = 11.20$ ,

Swollen:  $(8/25) * 28 = 8.96$ .

That is, the values of 11.20 and 8.96 will be used in calculating the % reductions in total joint counts, not the values of 10 and 8. Similar proration will be conducted for hands and wrists joint count.

**If the tender and swollen joint counts cannot be evaluated after proration, the tender and swollen joint count  $\geq 50\%$  improvement from baseline endpoint will be considered not met.**

### **Lupus anticoagulant**

**Lupus anticoagulant results will be derived as follows:**

- When activated partial thromboplastin time (aPTT)  $\leq 29.4$  seconds, then lupus anticoagulant is 'negative'.
- When aPTT  $\geq 29.4$  seconds and hexagonal phospholipid  $< 11$  seconds, then lupus anticoagulant is 'negative'.
- When aPTT  $\geq 29.4$  seconds and hexagonal phospholipid  $\geq 11$  seconds, then lupus anticoagulant is 'positive'.

**Lupus anticoagulant results will only be derived for baseline, week 24 and week 52 visits.**

#### **Dates**

Missing and incomplete dates will be imputed as outlined in [Appendix E](#).

#### **Laboratory Toxicity Grading**

**In cases when supplemental information for laboratory toxicity grading is missing or the result is ambiguous, the worse toxicity grade possible will be assigned.**

#### **Laboratory Measurements**

**Laboratory measurements that are below the lower quantification limits will be considered equal to the lower limit of quantification for all analyses unless explicitly noted otherwise.**

#### **8.4 Detection of Bias**

Important protocol deviations and early withdrawal from treatment and from study may bias the results of the study. The incidence of these factors will be assessed and reason for early withdrawals will be tabulated.

#### **8.5 Outliers**

Scatter plots will be examined to identify potential outliers in any of the continuous variables and frequencies of the categorical data will be examined to identify questionable values. The validity of any questionable values will be verified, and observations found to be due to data entry errors will be queried. Potential outliers that are not due to data entry error will be included in the analysis.

#### **8.6 Distributional Characteristics**

Not applicable.

#### **8.7 Validation of Statistical Analyses**

Programs will be developed and maintained, and output will be verified in accordance with current risk-based quality control procedures.

Tables, figures, and listings will be produced with validated standard macro programs where standard macros can produce the specified outputs.

The production environment for statistical analyses consists of Amgen-supported versions of statistical analysis software; for example, the SAS System version 9.4 or later.

## **9. Statistical Methods of Analysis**

### **9.1 General Considerations**

All categorical variables will be summarized using the number and percent of subjects falling into each category and all continuous variable will be summarized using mean, standard error (SE), standard deviation (SD), median, first quartile (Q1), third quartile (Q3), minimum, maximum, and number of subjects with observations. Safety endpoints will be summarized descriptively, including treatment-emergent adverse events and serious adverse events, clinically significant changes in laboratory values and vital signs, and incidence of antidrug antibodies. All safety analyses will be performed using the Safety Analysis Set based on subject's actual treatment received.

### **9.2 Subject Accountability**

The study dates for the first subject enrolled, last subject enrolled, last subject's end of IP **and** last subject's end of study will be presented.

The number and percent of subjects who were randomized, received investigational product, completed investigational product, discontinued investigational product and reasons for discontinuing, completed study, discontinued study and reasons for discontinuing study will be summarized overall and by randomized treatment group. Summary of subjects who discontinue investigational product/study due to COVID-19 control measures will be included.

### **9.3 Important Protocol Deviations**

Important Protocol Deviations (IPDs) categories are defined by the study team before the first subject's initial visit and updated during the IPD reviews throughout the study prior to database lock. These definitions of IPD categories, subcategory codes, and descriptions will be used during the course of the study. Eligibility deviations are defined in the protocol. The final IPD list will be used to produce the summary of IPDs table and the list of subjects with IPDs. IPDs related to COVID-19 control measures will be summarized separately.

### **9.4 Demographic and Baseline Characteristics**

The following demographic, baseline characteristics, baseline disease characteristics and baseline therapies of interest will be summarized descriptively by randomized treatment group.

Demographics:

- sex (female, male)

- age (years)
- age groups ( $\geq 18$  to  $< 50$ ,  $\geq 50$  and  $18 - 64$ ,  $65 - 74$ ,  $75 - 84$ )
- race (American Indian or Alaska Native, Asian, Black or African-American, Native Hawaiian or Other Pacific Islander, White, Other)
- ethnicity (Hispanic or Latino, Not Hispanic or Latino)
- geographic region (North America [Canada and United States] + Western Europe [Austria, France, Switzerland] + Asia Pacific [Hong Kong, Japan, South Korea and Taiwan], ROW [Bulgaria, Chile, Colombia, Greece, Italy, Mexico, Poland, Russia, Spain and Turkey])

Baseline characteristics:

- height (cm)
- weight (kg)
- body mass index (BMI) ( $\text{kg}/\text{m}^2$ )

Baseline disease characteristics:

- years since SLE diagnosis
- hSLEDAI score (continuous,  $< 10$  or  $\geq 10$ )
- baseline hSLEDAI organ involvement (CNS [seizure, psychosis, organic brain syndrome, visual disturbance, cranial nerve disorder, lupus headache, cerebrovascular accident], vascular [vasculitis], renal [urinary casts, hematuria, proteinuria, pyuria], musculoskeletal [arthritis, myositis], serosal [pleurisy, pericarditis], dermal [rash, alopecia, mucosal ulcers], immunologic [low complement, increased DNA binding], constitutional [fever], hematologic [thrombocytopenia, leukopenia])
- baseline BILAG domain score (A, B, C, D, E)
  - constitutional
  - mucocutaneous
  - neuropsychiatric
  - musculoskeletal
  - cardiorespiratory
  - gastrointestinal

- ophthalmic
  - renal
  - haematological
- CLASI activity score (continuous, 0, > 0 to < 8,  $\geq 8$ )
- total swollen and tender joint counts
- hand and wrist swollen and tender joint counts
- PGA VAS score
- baseline biomarkers
  - antinuclear antibody ( $\geq 1:80$  vs. negative or  $< 1:40$ )**
  - anti-dsDNA (continuous, positive, indeterminate or negative)**
  - C3, C4 complement (continuous, low or normal/high, low C3 or C4 vs. normal/high C3 and C4)**
  - anti-dsDNA and complement**
    - anti-dsDNA positive and low complement**
    - anti-dsDNA positive and normal/high complement**
    - anti-dsDNA indeterminate and low complement**
    - anti-dsDNA indeterminate and normal/high complement**
    - anti-dsDNA negative and low complement**
    - anti-dsDNA negative and normal/high complement**

#### Baseline medications

- immunosuppressant/immunomodulator (yes, no)
  - mycophenolate mofetil
  - azathioprine
  - methotrexate
  - anti-malarial (hydroxychloroquine, chloroquine, quinacrine)
  - dapsone
  - other
- daily OCS dose (prednisone-equivalent mg/day; **continuous, 0 mg/day, > 0 to < 10 mg/day,  $\geq 10$  mg/day**)

## 9.5 Efficacy Analyses

Unless stated otherwise, the Full Analysis Set (FAS) will be used for analysis of efficacy endpoints. The efficacy analyses are summarized in [Table 9-1](#), [Table 9-2](#) and [Table 9-3](#).

The SLE efficacy assessment data (BILAG, hSLEDAI, PGA, CLASI, swollen and tender joint counts, and [REDACTED]) will be submitted to an external independent committee comprised of clinicians with expertise in managing and assessing SLE disease and clinical trials for adjudication. The committee will adjudicate the data and determine whether the efficacy assessments are scored correctly and consistently based on the instruments' specifications.

Unless stated otherwise, the analysis of the SLE efficacy assessment data and their derived endpoints (SRI-4, BICLA, LLDAS and BILAG flare index) will be based on the data resulting from the adjudication. Additionally, **to assess the concordance between the investigators and adjudicators, the SRI-4 responses at week 16, 20, 24 and 52 based on the two sources will be cross-tabulated and** the concordance rate will be computed as the frequency of cases where the data based on the investigator's assessment and the data resulting from adjudication agree on classification of a subject as an SRI-4 responder/non-responder. If the concordance rate at week 52 is < 0.95, the primary endpoint may be **summarized** using SRI-4 responses derived based on the investigator-reported data **as a sensitivity analysis**.

**Table 9-1. Primary Efficacy Endpoint Summary Table**

Endpoint	Primary Summary and Analysis Method	Sensitivity and Supplementary Analysis
SRI-4 response at week 52	Within each treatment arm, the number and percentage of subjects achieving SRI-4 will be computed.	To assess different data sources: The primary analysis may be repeated using SRI-4 responses based on the investigator data, if the concordance rate is <0.95.

**Table 9-2. Secondary Efficacy Endpoint Summary Table**

Endpoint	Primary Summary and Analysis Method

• BICLA response at week 52

• LLDAS response at week 52

• Reduction of OCS to <math>\leq 7.5</math> mg/day by week 44 and sustained through week 52 in subjects with a baseline OCS dose <math>\geq 10</math> mg/day

• SRI-4 response at week 24

• BICLA response at week 24

• HSLEDAI reduction <math>\geq 4</math> points from baseline at week 24

• HSLEDAI reduction <math>\geq 4</math> points from baseline at week 52

	Number and percentage of subjects achieving response of interest will be summarized by randomized treatment arm.

• Improvement from baseline in tender and swollen joint count <math>\geq 50\%</math> at weeks 8, 12, 24, 36, and 52 in subjects with <math>\geq 6</math> tender and swollen joints involving the hands and wrists at baseline

• CLASI activity score <math>\geq 50\%</math> improvement from baseline at week 12, 24, 36, and 52 in subjects with a CLASI activity score <math>\geq 8</math> at baseline

	Number and percentage of subjects achieving response of interest will be summarized by randomized treatment arm.

• Annualized flare rate (as measured by BILAG score designation of “worse” or “new” resulting in a B score in <math>\geq 2</math> organs or an A score in <math>\geq 1</math> organ) over 52 weeks

	Descriptive statistics will be summarized by randomized treatment arm.

• Change from baseline in fatigue standardized score using the PROMIS Fatigue SF 7a at week 12, 24, 36, and 52

• Change from baseline in the physical component score, mental

	Descriptive statistics will be summarized by randomized treatment arm.

component score and individual domains of the SF 36 v2 at week 12, 24, 36, and 52	
• Change from baseline in the domain scores on the Lupus QoL at weeks 12, 24, 36, and 52	

